8.6 QUALITATIVE ANALYSES

Acceptability and feasibility of the systems navigation component will also be assessed through administration of brief behavioral surveys and qualitative interviews with approximately 20 study participants. The surveys will include, but not be limited to, questions about participants' attitudes/beliefs towards their interactions with the systems navigator, as well as other related topics such as their perceived risk for HIV.

Approximately 15 other key stakeholders will also be interviewed regarding the adoption and implementation of systems navigation as a strategy to improve HIV prevention integration in the STI clinic.

Participant in-depth interviews (IDI) will be scheduled to attempt to correspond with their final study visit (week 26, 39, or 52). When conducting a qualitative exploration, the sampling method should be designed to include a range of possible perspectives on the phenomenon under study, thus ideal qualitative samples are purposive in nature. For this study, we will utilize a purposive sampling strategy, which will allow for consideration of the concepts of range, saturation/redundancy, and stratification in the sampling frame. We will ask site staff to identify potential participants who would be interested in and comfortable with sharing their experiences in the study. Data on acceptability and factors affecting adherence will be collected during the IDI, including questions that explore the use and the acceptability of the systems navigation component. Additional interview topics will include challenges to study participation as well as risk perception. These interviews will be conducted by a trained study interviewer and will follow a semi-structured questionnaire guide. They will be approximately 60 minutes in duration and will be conducted in an area that maximizes participant privacy and confidentiality. Participants may be compensated for the completion of the in-depth interview. These interviews will be recorded for analysis and transcribed. Recording storage, tracking, and

management details will be described in the site's SOPs. These recordings will be stored in accordance with the longest requirement of any applicable regulations.

After transcription, all qualitative interviews will be translated into English (as needed), and then uploaded into a qualitative software analysis program (such as NVivo 12). The HPTN 112 Qualitative Team will follow a process of reading, coding, data display and data reduction in order to explore in greater depth participants' attitudes towards and experiences with the intervention. Data coding and analysis will be both iterative and interactive processes. The team will first read all interview transcripts in order to increase familiarity with the data. Next, the team will assign a priori codes and create emergent codes. Transcripts will then be re-read to create pattern codes that connect subsequent concepts under larger headings. Consistent patterns in meaning, concepts, and themes across all interviews will be identified, and detailed memos/data matrices will be developed to examine how participants' perceptions related to the intervention (i.e., ease of use, interactions with systems navigators, perceived efficacy) and to risk perception (i.e., motivations for participation, impact on partner or other social relationships) influence acceptability and interest in future use of a systems navigation component embedded in the clinic. Comparative analyses will be conducted to clarify differences that may exist for any subgroups of participants. Coding and analytic activities will be discussed during qualitative data analysis meetings, and discrepancies in coding and interpretation will be resolved through consensus.

See [Appendix II](#) for timing of interviews.

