Our preliminary work integrating oral PrEP into a Malawi STI clinic suggests acceptability of PrEP provision alongside STI services among heterosexual cisgender men, and enthusiasm for highly effective,^{11,12} and now approved for use long-acting injectable (LAI) PrEP. Likewise, published literature encourages an increase in integrated services to reduce the incidence of both HIV and STIs.¹³ Although the World Health Organization includes persons with STIs as a priority PrEP population,⁷ our ongoing study is one of the first to incorporate PrEP with STI clinics in sub-Saharan Africa (SSA).¹⁴ Reflecting the demographics of persons seeking testing, >60% of the 150 enrolled PrEP users in our cohort are heterosexual cisgender males (unpublished). Through this work, we have identified important gaps in PrEP service delivery including drop-off of referral from clinic staff (only 20% of all PrEP-eligible persons receiving STI services were offered PrEP) and poor PrEP persistence.

Besides demonstrating persistent HIV risk within this population, with nearly one-quarter of cisgender male participants having an incident gonorrhea or chlamydia infection during the 6 months of follow-up, this work has also started to identify important barriers to persistent PrEP use among heterosexual cisgender males who initiate PrEP.

Preliminary review of persistence data from an ongoing pilot study of PrEP in Malawi (unpublished) suggests that although 41/115 (35%) of cisgender men remained persistent on PrEP for 6 months after enrollment (adequate doses based on pill count and on-time follow-up consistent with adherence to daily oral PrEP), 17% were lost-to-follow-up immediately after initiating PrEP, and another 11% were lost-to-follow-up following their first (1-month) PrEP follow-up visit. Ongoing analysis of qualitative data from this same cohort suggests challenges with taking a pill every day, barriers in disclosing to friends and family, and changes in relationship status that influence perceived risk.

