2.1 PRIMARY OBJECTIVE(S)

- 2.1.1** To assess the effect of a systems-navigator facilitated HIV prevention package on PrEP persistence among cisgender heterosexual men seeking STI clinical services in Lilongwe, Malawi at 26 weeks.
- 2.1.2** To assess acceptability and barriers of implementing a systems-navigator delivered HIV prevention package among key stakeholders in the clinic and heterosexual cisgender men initiating PrEP at STI clinics.

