Throughout the study design, we distinguish between PrEP visits and study visits. PrEP visits are conducted on a timeline determined by the MoH and should align with the modality of PrEP that a participant has selected. During a PrEP visit, the navigator will meet with the participant, discuss risk and PrEP use, and offer POC STI testing to inform the risk discussion. Navigators will conduct tracing activities for any missed PrEP visit, in accordance to PrEP-user stated preferences for tracing (see [Section 5.0](#)). Study visits, on the other hand, occur every 13 weeks regardless of PrEP modality, and are completed by study nurses. These visits include in-depth behavioral surveys and specimen collection. Participants receive a financial incentive to attend and complete the study visits, and these visits continue regardless of a participant’s decision to continue or discontinue PrEP use. Tracing for missed study visits will utilize study staff – these staff members are distinct from Systems Navigators, who only trace for missed PrEP visits in the intervention arm. This distinction and separation is crucial to inform our primary outcomes (effect of navigation on PrEP persistence) and avoid contamination of interpreting the PrEP use outcomes in the context of financial incentives that are external to the study intervention.

In-depth qualitative interviews will be conducted with a subset of cisgender men who initiate PrEP (approximately 20 at last study visit) and with other key stakeholders (approximately 15) including persons involved in provision of navigation, STI or HIV care or prevention (including clinic management or oversight), or development of HIV prevention policy or programming at local or national level. The purpose of these interviews is to explore facilitators and barriers to acceptability of the intervention components.

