8.2.1 Primary Objective(s) and Endpoints

8.2.1.1 To assess the effect of a systems-navigator facilitated HIV prevention package on PrEP persistence among heterosexual cisgender men seeking STI clinical services in Lilongwe, Malawi at 26 weeks.

Consistent with this primary study objective, the following endpoint(s) will be assessed: Persistent PrEP use across all three modalities (LAI, daily oral, or event-driven PrEP), where persistence is defined as adherence to any PrEP modality through 26 weeks, comparing proportions in intervention and control arm participants.

- (LAI) receive on-time injections (+/- 7-day window for the first injection and 14-day window thereafter)
- (Daily Oral) have protective PrEP concentration detected at designated study follow-up visits, based on intraerythrocytic TFV-DP collected as DBS; TFV-DP concentrations associated with ≥ 4 doses/week will be classified as adherent.

- (Event-driven) self-reported PrEP adherence (2+1+1), in the past 30 days, assessed through self-report of PrEP use and sex acts at study follow-up visits, and intraerythrocytic TFV-DP concentrations.

8.2.1.2 To assess acceptability and barriers of implementing a systems-navigator delivered HIV prevention package among key stakeholders in the clinic and heterosexual cisgender men initiating PrEP at STI clinics.

Consistent with this primary study objective, the following endpoint(s) will be assessed among participants in the intervention arm only:

- Engagement with system navigators:
 - Overall: Proportion of intervention arm participants engaged by systems navigator within 7-days of enrollment visit (defined as any contact, i.e. text exchange, in-person communication)
 - Overall: Proportion of intervention arm participants engaged by systems navigators at least once after the initial engagement during the first 26 weeks following initiation of PrEP.
 - Overall: Proportion of intervention arm participants with attempted engagement by systems navigators at least once after the initial engagement during the first 26 weeks following initiation of PrEP.
 - Overall: Mean (standard error) number of contacts (text, telephone call, home visit, other) with intervention arm participants made with systems navigators (mean contacts per participant) during first 26 weeks following initiation of PrEP.
- Uptake of self-test/pill pack (“re-start” kit) among those to whom it is distributed (through end of study participation):

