 - Proportion who self-report use of HIV self-test
 - Proportion who self-report use of PrEP pill pack
 - Proportion who self-report use of HIV self-test in conjunction with/prior to initiation of PrEP pill pack
- Acceptability and barriers among key stakeholders, including participants enrolled as seronegative PrEP initiators and other key stakeholders:
 - Acceptability based on quantitative surveys (participants enrolled as seronegative PrEP initiators only)
 - Perceived facilitators and barriers to implementation of the intervention will be assessed through individual semi-structured interviews.

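### Section 8.6 selects interviewees only by staff nomination of interested, comfortable men, which may under-represent those who disengaged from PrEP or from the navigator

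*Protocol*

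**What the plan says.** The second primary objective (Section 2.1.2) reads: "To assess acceptability and barriers of implementing a systems-navigator delivered HIV prevention package among key stakeholders in the clinic and heterosexual cisgender men". Section 8.2.1.2 limits its endpoints to the intervention arm and names the source for this part: "Perceived facilitators and barriers to implementation of the intervention will be assessed through individual semi-structured interviews".

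On participant interviews, Section 8.6 of the protocol states:

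- an aim: "the sampling method should be designed to include a range of possible perspectives on the phenomenon under study";
- a method: "we will utilize a purposive sampling strategy, which will allow for consideration of the concepts of range, saturation/redundancy, and stratification";
- one operational step: "We will ask site staff to identify potential participants who would be interested in and comfortable with sharing their experiences in the study".

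On timing, Section 3.0 plans interviews with "approximately 20 at last study visit". Section 8.6 is softer and says only that scheduling will try to match the final visit. The interview footnote in Appendix II names weeks 26, 39 and 52 and does not mention early termination.

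For the roughly 15 other stakeholders, Section 4.3 names the dimensions of variety it wants (role, responsibility, exposure to the intervention). For the roughly 20 participants, no dimension is named.

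**The concern.** The one step that is spelled out pulls against the aim it serves. Men whom site staff judge interested and comfortable will tend to be those who attend and get on well with staff. Men who stopped PrEP, had to be traced or avoided the navigator are less likely to come to mind.

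Those men matter more than their numbers suggest. Two components of the package, tracing for missed PrEP visits (Section 5.2) and the re-start kit (Section 5.4), are used only when a man misses a visit or stops PrEP. Section 5.4 itself expects most men who stop to do so by not attending. If they are thin in the interview sample, acceptability may look better and barriers fewer than they are, in a pilot meant to inform a larger trial. Section 8.6 also plans comparisons between subgroups of interviewees, but no sampling rule ensures that those subgroups are present.

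**Working it through.** The plan gives no figure for the make-up of the interview sample, only its approximate size of 20. Two questions can be separated: what final-visit timing does, and what nomination does.

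**Timing.** Inputs:

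- 200 men randomised 2:1 (Section 8.1), so 200 × 2/3 ≈ 133 in the intervention arm;
- 10% lost by week 26 (Section 8.3), assumed equal in both arms, so 0.10 × 133 = 13.3 lost and 119.7 retained;
- SOC persistence 40% plus a targeted difference of 15 to 35 points (Section 8.3), so intervention persistence p of 55% to 75%; 65% is the midpoint.

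Section 8.5.1 counts only retained men as persistent, so lost men are first taken as non-persistent. Then non-persistent = 133 × (1 − p), still on study = that number − 13.3, and the expected number in a random 20 of retained men = 20 × (still on study) / 119.7.

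| p | Non-persistent | Still on study | Share still on study | Expected in 20 |
|---|---|---|---|---|
| 55% | 59.9 | 46.6 | 78% | 7.8 |
| 65% | 46.6 | 33.3 | 71% | 5.6 |
| 75% | 33.3 | 20.0 | 60% | 3.3 |

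The 13.3 lost men are 22% to 40% of non-persisters (13.3/59.9 to 13.3/33.3). If p is instead read as the rate among retained men, which is how the working sample of 180 in Section 8.3 treats it, the expected numbers are 20 × (1 − p) = 9, 7 and 5. Non-persistent men still on study are then 119.7 × (1 − p) = 53.9, 41.9 and 29.9. With the 13.3 lost men added to the denominator, the shares reachable are 80%, 76% and 69%.

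So timing leaves most non-persistent men within reach. Non-persistence is wider than stopping PrEP, because it also covers low drug levels and late injections. These counts are therefore only a guide to the number of men who disengaged.

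**Nomination.** The protocol holds nothing from which its effect can be estimated. For illustration only, suppose a non-persistent man is half as likely to be nominated as a persistent one, with p among retained men. The expected number in 20 is then 20 × 0.5(1 − p) / [0.5(1 − p) + p]:

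- p = 55%: 20 × 0.225/0.775 = 5.8, against 9 with no selection;
- p = 75%: 20 × 0.125/0.875 = 2.9, against 5 with no selection.

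The factor of one half is an assumption. Staff who sought out men who had stopped PrEP would move the numbers the other way. Nothing in Section 8.6 asks them to.

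**The case against.** The strongest reply is that the protocol separates leaving PrEP from leaving the study. Study visits carry an incentive and continue whatever a man decides about PrEP (Section 3.0). Missed study visits are traced by phone and then in person (Section 4.5.2). A final evaluation is sought from early leavers (Section 4.6). The sample is declared purposive with stratification in view, and nomination may operate within that. Barriers also come from a questionnaire, navigator forms and logbooks, and other stakeholders (Section 6.6), and navigators record risk and PrEP use at tracing contacts (Section 5.3). Any voluntary interview reaches only willing men.

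Much of this stands. A reader might infer that disengaged men are filtered out, but the documents do not support that.

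A reader might also lean on the earlier cohort, where "17% were lost-to-follow-up immediately after initiating PrEP, and another 11% were lost-to-follow-up following their first (1-month) PrEP follow-up visit". Those are losses from PrEP care in a different study without this trial's separate study visits, so they do not measure who could be interviewed here.

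A third tempting reading is that about 7 of the 20 interviews (20 × 1/3 = 6.7) would go to SOC men. That assumes a random draw from both arms, whereas the sample is purposive, Section 8.2.1.2 confines the navigation endpoints to the intervention arm, and SOC interviews could serve objective 2.3.7.

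What the reply does not remove is that considering stratification commits to no stratum, while nomination is a stated step. The other sources compensate only in part. Navigator records depend on contact with the navigator, and the other stakeholders deliver services or set policy rather than use PrEP.

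**Conclusion.** The concern holds as a risk of under-representation. The stated selection step works against the section's own aim, for interviews that are the named source on facilitators and barriers in a primary objective. The size of the effect of nomination cannot be derived from the protocol.

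Timing is a minor part. On the assumptions of Section 8.3, with loss equal across arms, it mainly misses the roughly 10% lost from the study. No stated figure in the plan is wrong. This is worth changing because the remedy is cheap and the interviews inform the design of a larger trial.

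**What to change.** In Section 8.6, replace nomination on interest and comfort with candidates identified from study records by named strata of intervention-arm men:

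- men who persisted on PrEP;
- men who stopped PrEP or were traced for missed PrEP visits;
- men who were offered a re-start kit.

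Reserve a minimum number of the approximately 20 places for the second and third groups; the team should set that number. State that interviews on the acceptability of navigation are with intervention-arm men, in line with Section 8.2.1.2, and say how many SOC interviews, if any, serve objective 2.3.7. Record refusals by stratum. In Appendix II, allow the interview at the early-termination visit.

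The cost is wording in Section 8.6 and the Appendix II footnote, plus somewhat more effort to schedule disengaged men. The number of interviews and the interviewer do not change. Participation stays voluntary, and a man's comfort is protected by his own right to decline (Section 6.6).

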9.0 LABORATORY SPECIMENS AND BIOHAZARD CONTAINMENT

Laboratory procedures are described below and in [Appendix II](#) and [Section 6.2.1](#); tests to be performed at a subsequent visit for participants who have a reactive or positive HIV test interpretation are described in [Appendix III](#).

9.1 LOCAL LABORATORY SPECIMENS

As described in [Section 6](#), the following types of specimens will be collected at the local laboratory (LL):

- Blood
- Urine

As described in [Section 6](#), the following types of testing will be performed at the local laboratory (LL):

- HIV rapid antibody testing
- HIV RNA (Enrollment)
- STI testing for syphilis (RPR and reflex to TPPA, if appropriate)
- STI testing for CT/NG

LLs will perform HIV and STI testing as indicated in Appendices II-IV. All STI test results obtained through study visits, including POC STI testing through systems navigators, will be returned to HIV seronegative participants. Some results will not be returned same day, however, participants who test positive for an STI at study visits will be informed of their result and be referred for treatment as per local guidelines. For HIV seronegative participants, HIV RNA testing will typically be tested within 7-10 days of enrollment. Participants will be informed if this result is consistent with HIV infection, despite negative rapid antibody testing at enrollment.

The study site must adhere to the HPTN Manual of Operations (MOP), the SSP Manual, and local SOPs, for proper collection, processing, labeling, transport, and storage of specimens to the LL. Non-US laboratories performing these tests will be monitored by an External Quality Assurance (EQA) provider or specified quality assurance contractor. In addition, each study site must adhere to the Requirements for Laboratories in Performing Testing for DAIDS-Supported and/or Sponsored Clinical Trials policy (DAIDS-OD-A-POL-00002) as outlined in the DAIDS SCORE Manual and the DAIDS Good Clinical Laboratory Practice (GCLP) as appropriate. Laboratories must also follow the DAIDS Clinical Research Laboratory and Specimens Management policies at <https://www.niaid.nih.gov/research/daids-clinical-research-laboratory-specimens-management>. Specimen collection and storage at the local laboratory will be documented using the Laboratory Center Specimens Management System (LDMS) as described in the SSP Manual.

9.1.1 Specimen Storage at Study Site

Sites will provide short-term storage of blood (plasma, DBS) and urine to facilitate batched testing. Stored samples will be shipped to the HPTN LC (located in the US) for Quality Assurance (QA), as well as measurement of antiretroviral drugs from DBS or plasma. Stored samples may also be used for characterization of HIV in participants who acquire HIV, additional testing of STI pathogens, and evaluation of laboratory assays related to the study objectives. Specifically, these tests are conducted to characterize factors associated with HIV and STI infection, and virologic, pharmacologic and immunologic responses among men initiating PrEP at Bwaila STI clinic. Testing on stored samples will be performed by the HPTN LC or another laboratory selected and approved by the HPTN LC. Samples stored at study sites may not be used for LL testing not otherwise specified in the protocol without written approval by the HPTN LC and appropriate regulatory body prior to use.

Stored samples may be maintained at the site until the study is complete. The HPTN LC will communicate with sites when samples can be destroyed; sites will follow LL policies for sample destruction. A list of samples to be destroyed will be provided by the SDMC, which will be reviewed and reconciled by the site as part of the sample destruction process.

9.1.2 Virology

HIV testing will be performed by local laboratories and will follow Malawi Ministry of Health algorithms.

Additional virologic assays may be performed to address study objective 2.3.5 at the HPTN LC or a laboratory designated by the HPTN LC. This testing may include the following tests for participants who acquire HIV infection: HIV viral load, HIV resistance testing, HIV subtyping, and other tests to characterize HIV viruses and/or the host response to HIV infection. Further, the HPTN LC may perform HIV RNA testing at study visits with stored samples from individuals who do not acquire HIV during the study. Results will not be returned to the sites or study participants, except for HIV diagnostic testing (if results obtained at the HPTN LC do not agree with site results).

Resistance testing may be performed at the HPTN LC or a laboratory selected by the HPTN LC. Results of this testing will not be returned to study sites.

